### **8.2.3 Other medical devices or medication to be used**

The ARGOS-SC system is the only investigational medical device that will be used during this study. No other devices or medications will be used specifically for this clinical investigation. Standard devices will be used as required for ophthalmic diagnostics and treatment procedures, including if needed glaucoma treatment.

## **8.3 Subjects**

### **8.3.1 Inclusion Criteria**

Subjects of the ARGOS-SC01 clinical investigation with an implanted ARGOS-SC pressure sensor.

### **8.3.2 Discontinuation or Withdrawal Criteria**

#### **8.3.2.1 Study stopping rules**

The study may be discontinued at any time for administrative reasons; if new negative data about the investigational device resulting from this or any other study becomes available; and/or on the recommendation of the sponsor, the investigators, and/or the EC or regulatory authorities.

 Implantata Ophthalmic Products GmbH	Clinical Investigation Plan ARGOS-SC01_Follow-up	Revision C  Page 56 of 97
--	---	---------------------------------

If the study is prematurely terminated or suspended, the sponsor will promptly inform the investigators, the Regulatory Authorities and the ECs of termination or suspension and the reason behind it. If the study is prematurely terminated for any reason, the investigator should promptly inform the site's study subjects and assure they receive appropriate therapy and/or follow-up.

The study can be terminated at any time for any reason by the sponsor.

#### **8.3.2.2 Premature subject withdrawal**

Subjects will be informed that they have the right to withdraw from the study at any time. The investigator must determine whether voluntary withdrawal is due to a cause that could raise safety concerns.

All subjects who withdraw from the study after inclusion in the study and before completing the follow-up visits per protocol will be considered to be drop-outs. Subjects who drop-out or are withdrawn after implantation will not be replaced. Unless the patient revokes his/her permission to use it, any data collected up to the point of the patient's withdrawal will be included in the analysis. The data of all subjects who undergo implantation of the ARGOS-SC pressure sensor will be included in the efficacy analysis under the Full Analysis Set.

A subject will be withdrawn for any of the following reasons:

- The subject withdraws informed consent.
- The ARGOS-SC pressure sensor must be removed for any reason.

If the subject permits, all end-of-study assessments indicated in the visit schedule will be performed for implanted early discontinuing subjects.

Any subject who has been discontinued from the study because of an AE related to a study device or procedure will be followed as deemed appropriate by the investigator until resolution or stabilization of the event. This will be documented in the medical chart and in the CRF. Any subject who has been discontinued from the study because of an AE not related to a study device or procedure will be followed as deemed appropriate by the investigator.

 Implantdata Ophthalmic Products GmbH	Clinical Investigation Plan ARGOS-SC01_Follow-up	Revision C  Page 57 of 97
---	---	---------------------------------

The investigator will classify the termination reason of each subject at the end of the study in the termination page of the CRF according to the following:

- AE
- Non-compliance with clinical investigation plan (CIP)
- Lost to follow up
- Voluntary withdrawal not for AE
- Other reason

The choice of keeping the implant or letting the implant be retrieved will be offered to the participating patients.

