### 8.3.16 Semiannual Follow-up visits V10 – V13 (Month 18 – Month 36)

Procedures to be conducted at the visits include:

- Recording of AEs/SAEs/ADEs/SADEs, concomitant medications and device malfunctions
- VQoL questionnaire (V11, V13)
- User acceptance questionnaire (Investigator) (V13)

 Implantdata Ophthalmic Products GmbH	Clinical Investigation Plan ARGOS-SC01_Follow-up	Revision C  Page 68 of 97
---	---	---------------------------------

- User acceptance questionnaire (patient) (V13)
- Visual acuity (ETDRS) (OU)
- External eye photography
- Heidelberg Engineering ANTERION® (if available)
- Perimetry (OU)
- Anterior Segment assessments: slit-lamp biomicroscopy, AS-OCT), gonioscopy (OU)
- Posterior Segment assessments: funduscopy, PS-OCT, fundus photography (V11, V13) (OU)
- IOP Measurement: GAT (OU) and ARGOS-SC. If available: Pascal DCT (OU)
- Patient ARGOS-SC self-measurements
- Remind subjects to promptly report any SAE that may occur at any time during the study.
- Complete the CRF and arrange the next visit.

Visit 13 is the study discharge/end of study visit. After this visit, subjects will return to standard care. The choice of keeping the implant or letting the implant be retrieved will be offered to the participating patients.

 IOP Implantdata Ophthalmic Products GmbH	Clinical Investigation Plan ARGOS-SC01_Follow-up	Revision C  Page 69 of 97
--	---	---------------------------------

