#### **9.5 Criteria for termination of the clinical investigation**

The participation of an individual site in the study will be discontinued if the sponsor, the investigator or the responsible ethics committee deems it necessary for any reason.

The complete study will be discontinued:

- If the sponsor and/or any responsible regulatory authority or ethic committee judges it necessary for any reason. See also Section 8.3.2 Discontinuation or Withdrawal Criteria Early Patient Withdrawal and Section 11.11 Criteria for Suspension and Premature Termination of Study

---

 In the unprobeable case this number of measurement pairs is not reached, the primary objective is to be adjusted according to the actual number of measurement pairs.

 IOP Implantata Ophthalmic Products GmbH	Clinical Investigation Plan ARGOS-SC01_Follow-up	Revision C  Page 71 of 97
---	---	---------------------------------

- If, throughout the course of the study, the DSMB comes to the conclusion that the ARGOS-SC pressure sensor would expose the subject study patients to undue risk

All patients will continue to be followed up. If the study is discontinued for safety reasons it will be proven whether explantation of all ARGOS-SC sensors deems necessary or follow-up of patients is sufficient.

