### **10.3 Recording of Adverse Events (AEs)**

All AEs will be documented throughout the clinical trial as per ISO 14155, chap. 7.4.1, meaning from the point of inclusion/signing of the informed consent, until resolution or stabilization, or for a maximum of 7 days after the last subject has been discharged from the study.

All AEs will be reported on an Adverse Event Form, one for each Adverse Event, which is part of the CRF.

AEs will be collected with a non-leading question at each visit: "Have you had any new or worsening health problems since the last visit?" as well as by reporting those events directly observed and spontaneously reported by the subject. Clearly related signs, symptoms and abnormal diagnostic procedures should preferably be grouped together and recorded as a single diagnosis or syndrome whenever possible. Seriousness, severity (mild, moderate or severe), outcome and relationship to investigational device as well as expectedness and action taken will be recorded in the AE page of the CRF. Start and end date and time of the event will also be recorded. SAEs will be followed until resolution or stabilization. AEs will be followed until resolution or stabilization, or for a maximum of 7 days after the last subject has been discharged from the study.

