8.6.1 Safety

- Number of patients experiencing a device-related SAE (SADE) from V09 (month 12) to V13 (month 36). This parameter will be analysed using a frequency table.
- Incidence, nature, severity and seriousness of observed adverse events and adverse device events at any time from V09 (month 12) throughout V13 (month 36). This parameter will be analysed using a frequency table.

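### Sensor removal ends study participation, so new adverse events after removal may go unrecorded while the patient still counts in the month-36 safety denominator

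*Protocol*

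**What the plan says.** **Withdrawal rule.** Protocol 8.3.2.2 gives two reasons for which a subject will be withdrawn. One is withdrawal of consent. The other is "The ARGOS-SC pressure sensor must be removed for any reason".

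**What is kept.** The same section states that "any data collected up to the point of the patient's withdrawal will be included in the analysis", unless the patient revokes permission. Protocol 9.8 evaluates early terminators like completers. SAP section 6 defines a single analysis set, the FAS, with no exclusion for explantation, and SAP 8.8.1 runs all safety analyses on it.

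**What happens after withdrawal.** Protocol 8.3.2.2 says: "If the subject permits, all end-of-study assessments indicated in the visit schedule will be performed for implanted early discontinuing subjects". A subject discontinued for a device- or procedure-related AE is "followed as deemed appropriate by the investigator until resolution or stabilization of the event", with documentation in the chart and CRF. For an unrelated AE, follow-up is at the investigator's discretion with no stated end. For removal without an AE, nothing further is stated.

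**What is analysed.** SAP 8.6.1 takes as a secondary safety endpoint "Number of patients experiencing a device-related SAE (SADE) from V09 (month 12) to V13 (month 36") and, beside it, AE incidence over the same period. SAP 8.1.2.1 bases percentages on all subjects in the analysis set. SAP 7.3 analyses dropouts as far as they are documented.

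**The concern.** Withdrawal of consent is the patient's decision to stop being observed. Removal of the sensor ends only the ability to take ARGOS-SC readings; it gives no reason to stop asking about adverse events. By treating the two alike, the protocol ends planned safety observation because of something that happened to the device, in a study whose stated purpose is long-term safety and performance.

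The observation lost matters because explantation is itself an operation on the eye. Protocol 8.3.13.1 describes a scleral incision of 4.5 to 5 mm, viscoelastic in the suprachoroidal space and at least one suture. The AEs of particular interest in Protocol 7.3 include suprachoroidal hemorrhage, choroidal and retinal detachment, and hypotony defined partly by lasting more than one month, a duration that a single exit visit cannot establish.

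If such events are not sought, the safety tables show the patient as event-free for months in which nobody was scheduled to look.

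**Working it through.** **Step 1. Which events are covered after a removal?**

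- *Event at or before removal.* Recorded and counted. Device removal is one of the action-taken categories for an AE (Protocol 10.3.4). If the event is a SADE, the patient is already in the endpoint count, and later events cannot change it.
- *The event that caused discontinuation, if device- or procedure-related.* Followed to resolution or stabilization and entered in the CRF (8.3.2.2).
- *SAEs already known.* Followed to resolution or stabilization (11.13).
- *New SAE after removal.* Reportable to the sponsor whatever its cause, once the site knows of it (10.5). No scheduled visit remains at which the site would learn of it.
- *New non-serious AE after removal.* Protocol 10.3 collects AEs by a question at each visit, by direct observation and by spontaneous report. With no visits, spontaneous report is the main route left.
- *Removal without an AE.* Nothing is stated beyond the end-of-study assessments.
- *The end-of-study assessments.* Offered to *implanted* early discontinuing subjects. The text does not say whether a subject already explanted qualifies.

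The gap is therefore new events between removal and month 36.

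**Step 2. How does the SAP treat those months?** The denominator is the full FAS (SAP 8.1.2.1). Study duration is derived (SAP 7.1) and listed (Listing 2), but it enters no rate. Unobserved time therefore counts as event-free, and any error lowers the incidence.

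**Step 3. Size.** The plan has no figure of its own to reproduce: it gives neither a removal rate nor a SADE rate, and 24 is a ceiling that was not calculated (Protocol 9.2). The following is illustration.

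Inputs from the documents: at most 24 patients (Protocol 8.3.6) and 24 months each (8.3.5). Assumptions: all 24 enroll; 1 to 3 sensors are removed; 6 to 18 months remain at removal.

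Total planned observation = 24 × 24 = 576 patient-months.

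Loss = removals × months remaining:

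- low: 1 × 6 = 6; 6/576 = 1.0%
- middle: 2 × 12 = 24; 24/576 = 4.2%
- high: 3 × 18 = 54; 54/576 = 9.4%

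Each patient whose first SADE falls after removal and is missed lowers the count by 1, or 1/24 = 4.2 percentage points. Exact (Clopper-Pearson) two-sided 95% limits for x of n are the 0.025 quantile of Beta(x, n − x + 1) and the 0.975 quantile of Beta(x + 1, n − x). For x = 0 the lower limit is 0 and the upper limit is 1 − 0.025^(1/24) = 14.2%.

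| Patients with a SADE | Percent | 95% CI |
|---|---|---|
| 0/24 | 0.0 | 0 to 14.2 |
| 1/24 | 4.2 | 0.1 to 21.1 |
| 2/24 | 8.3 | 1.0 to 27.0 |
| 3/24 | 12.5 | 2.7 to 32.4 |

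The SAP plans only a frequency table for this endpoint; the intervals are added here to show what one event does at this sample size. A patient already counted with a SADE contributes a shift of zero.

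**The case against.** The strongest reply is that nothing in the protocol says AE recording stops when one patient is withdrawn. Section 10.3 sets the outer limit as resolution or stabilization, "or for a maximum of 7 days after the last subject has been discharged from the study". That limit is study-wide, and the section accepts spontaneous reports. All SAEs go to the sponsor regardless of relationship, and explantation must be notified to the sponsor immediately (8.3.13.1). To miss a SADE in the endpoint, a patient must have none at or before removal, have a first one afterwards, and slip past every one of these routes. A malfunctioning sensor may also stay in place (8.3.13.1), so removals may be few. The endpoint is secondary and descriptive.

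Much of this stands, and it limits the size of the point. It does not close the gap. A recording window without visits depends on the patient volunteering information or the site happening to learn of an event. Section 8.3.2.2 speaks of following the triggering event only, so sites could reasonably read the two sections differently. The AE incidence endpoint is more exposed than the SADE count, because non-serious events are the least likely to be reported unprompted.

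It is also fair to say that a complication of explantation is not automatically a SADE: it must be judged device-related and meet a seriousness criterion. It would still be an AE.

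**Conclusion.** The point holds as a gap in data collection that can bias SADE and AE incidence downward. Its size rests on assumptions, because the documents give no removal rate: with 1 to 3 removals among 24 patients and 6 to 18 months remaining, 1.0% to 9.4% of planned observation is lost, and each first SADE missed moves the endpoint by 4.2 percentage points. It is worth correcting because one event matters at this sample size and the remedy is simple.

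A reader might infer more than the documents support:

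- *That explanted patients leave the safety endpoint.* They do not. They remain in the FAS, their data to withdrawal count, and a SADE that prompts removal is counted.
- *That observation stops at the moment of highest risk.* The reviewed text gives no event rate by time or after explantation. Protocol 8.3.13.1 links explantation to medical risk, but the withdrawal rule covers any reason.
- *That Protocol 9.5 contradicts 8.3.2.2.* The statement "All patients will continue to be followed up" concerns termination of the whole study, which is a different situation from one subject's withdrawal.
- *That retrieval at V13 biases the endpoint.* Section 8.3.16 says "The choice of keeping the implant or letting the implant be retrieved will be offered to the participating patients", but at the discharge visit this falls after the V09 to V13 window. The 7-day limit also runs from the last subject's discharge: with 36 months overall and 24 per subject, an early finisher could be up to about 36 − 24 = 12 months from it.

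Whether and when to explant is not at issue.

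**What to change.** 1. **Protocol 8.3.2.2.** Separate two cases. When the sensor is removed, performance measurements end. When consent is withdrawn, participation ends.
2. **Visits.** With the patient's consent, continue AE and SAE recording at the remaining scheduled visits to V13 after removal, whatever the reason for removal.
3. **Exit assessments.** State whether *implanted* early discontinuing subjects include those already explanted.
4. **Protocol 10.3.** State that AE recording continues after sensor removal, so that it agrees with 8.3.2.2.
5. **SAP.** List explanted patients with date of removal and time observed. Listing 2 already carries study duration, so this is a flag and a date.

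**Cost.** The change alters follow-up obligations, so it needs a protocol amendment with ethics and authority review (Protocol 11.4) and possibly renewed consent (11.1). In practice it adds at most four visits (V10 to V13, if removal comes before V10) for a few patients. Protocol sections 5 and 6.2 describe study follow-up as close to routine glaucoma care, so the added burden should be small.

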#### **8.3.2.3 Completed Subjects**

A completed subject is considered to be a subject that completed all procedures as defined by the clinical investigation plan.

#### **8.3.2.4 Subjects lost to follow-up**

If a subject fails to appear for a follow-up examination, reasonable effort should be made to locate or contact them to at least to determine their health status while fully respecting the subject's rights, followed by mandatory contacts with the patient's treating doctor for exchange information on the patient's health status. Reasonable effort consists of at least three attempts to contact the subject by phone or post. These efforts should be documented in both the subject's source documents and CRF. So that the monitor can verify if the study center's attempted contacts with the patient and patient's family doctor were adequate.

#### **8.3.3 Point of enrollment**

A subject is considered as being enrolled into the clinical investigation when he/she gives written consent to participate in this investigation.

#### **8.3.4 Total expected duration of the clinical investigation**

The estimated total duration of the study from first patient screened to last patient last visit is 36 months.

---

 The study duration of the ARGOS-SC01\_Follow-up study is expected to be 36 months, as the overall recruitment for the ARGOS-SC01 study is expected to be finished by the end of February 2020, therefore the last patient will not be completed until February 2021 with V09, which is the V01 of the ARGOS-SC01\_Follow-up study.

 IOP Implantata Ophthalmic Products GmbH	Clinical Investigation Plan ARGOS-SC01_Follow-up	Revision C  Page 58 of 97
---	---	---------------------------------

### **8.3.5      Expected duration of each subject's participation**

The maximum duration of each subject's participation in this clinical intervention is 24 months. The point of enrollment is considered to be the last Visit 09 of the ARGOS-SC01 clinical trial.

### **8.3.6      Number of subjects required**

This exploratory investigation will enroll maximal 24 patients.

### **8.3.7      Informed Consent**

Eligible patients may only be included in the study after providing written informed consent as described in Section 11.1. Failure to obtain signed informed consent renders the patient ineligible for the study.

### **8.3.8      Allocation of Patient Number**

Each subject is uniquely identified in the study by a combination of his/her country identifier, site number and patient number. The number will be the same number as in the ARGOS-SC01 clinical trial.

### **8.3.9      Methods and timing for assessing, recording, and analyzing parameters**

During the study, subjects will attend 4 clinic visits (V10 – V13). The Baseline Visit is V09, the last visit of the ARGOS-SC01 clinical investigation. The assessment schedule in summarizes all visits and the assessments to be performed at each. The visit window given in the table should be adhered to as closely as possible.

### **8.3.10     Safety**

At each follow-up visit, the Investigator will examine the subject and record information about any new or ongoing adverse events, adverse device events or clinically significant anomalies. In addition, the Investigator or designated site staff will ask the subject non-leading questions to ascertain if the subject experienced any adverse events or adverse device events between visits.

### **8.3.11     Performance**

IOP level will be assessed at every follow-up visit in a series of 2 GAT standard measurements followed by 3 consecutive measurements with the ARGOS-SC system and if available, additional 2 DCT measurements followed by 3 consecutive measurements with the ARGOS-SC system.

Patients were given a MESOGRAPH reading device at Visit 01 in order to measure the IOP daily at home. Measurements shall be taken at least 4 times per day (morning, noon, afternoon, evening). The

 IOP Implantata Ophthalmic Products GmbH	Clinical Investigation Plan ARGOS-SC01_Follow-up	Revision C  Page 59 of 97
---	---	---------------------------------

MESOGRAPH reading device will be connected to an external GSM module, which will transfer the measured value directly to a secure database. Investigators can log into the database in order to track the pressure levels of their patients as required. At every follow-up visit, site staff will examine the subject's hand-held reader device and download all readings recorded since the last visit. In addition, they will ask subjects non-leading questions to determine if any device deficiencies occurred since the last visit. All device deficiencies will be recorded on the device deficiency page of the CRF. To ensure accuracy and comparability of the recorded parameters, all responsible site personnel will be thoroughly instructed on the agreed measurement methods.

To access the user acceptance of the general usability of the ARGOS-SC system, physicians and personnel performing the ARGOS-SC system measurements will be asked to complete user acceptance questionnaires. The aim of these questionnaires is to gain more information about the level of user-acceptance of the ARGOS-SC system during IOP measurement. The data collected with these questionnaires is only of exploratory nature and will not be included in the analysis. Results will provide the sponsor with data that could influence future device system improvements.

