#### **3.3 Measurement of IOP**

Ensuring whether maintenance of target IOP is adequate requires frequent monitoring using an IOP measuring device. There are several tonometric devices on the market, which can be categorized based on whether or not they involve direct corneal contact.

Weighing all limitations of currently available methods for estimating/measuring IOP, the Goldmann Applanation Tonometer (GAT), even though it's development dates back into the 1950's, still represents the gold standard technique for measuring the IOP, necessitating for the treating

 IOP Implantdata Ophthalmic Products GmbH	Clinical Investigation Plan ARGOS-SC01_Follow-up	Revision C  Page 19 of 97
---	---	---------------------------------

ophthalmologist to weigh all influencing factors. During the last couple of years, there has been an effort to establish the Pascal Dynamic Contour Tonometer as an alternative to GAT. Both methods are regulatory approved methods:

*Goldmann Applanation Tonometer*

Goldmann Applanation Tonometry was first described in the 1950's [5, 6]. Like all applanation tonometers, it is based on the Imbert-Fick principle that the external force needed to flatten a portion of a sphere is proportional to the pressure within the sphere resisting the deformation [7]. Although it is considered to be the gold standard method to which all others IOP-Measurements are compared, GAT is limited by several factors. Corneal anaesthesia is required because the probe touches the cornea, which likewise raises the risk of infection and corneal abrasion [8]. The force needed to applanate the eye is also influenced by biomechanical properties of the cornea (thickness, rigidity, deformation), sclera and surface tear film, all of which can vary and are not fully characterized, making it difficult to correct for differences seen when these properties are outside normal ranges [2] [9–11]. For example, GAT is likely to under- or overestimate IOP in patients with thinner or thicker than average corneas [8].

Repetition of readings in short intervals, or other application of other pressure to the eye, such as pulling the eyelid up, can create artifacts. A skilled operator is required to perform the measurement, which is still prone to operator biases such as digit bias and bias towards the norm.

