#### 8.1.2 Description of the measures to be taken to minimize or avoid bias

All eligible patients will be enrolled.

There will be no control group for safety events. Incidence, nature and severity will be compared to literature of standalone NPGS. To allow assessment of performance, measurements of IOP with the ARGOS-SC sensor will be compared to those obtained with the standard GAT method and Pascal DCT at the same time point. To prevent possible influence of prior knowledge of the IOP value obtained with the ARGOS-SC, which is objectively displayed, measurements will always be made first with GAT/DCT. Data on all device deficiencies will be recorded.

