#### **8.3.12.5 Acceptance Questionnaires ARGOS-SC**

In the study, two types of questionnaires will be used to assess potential strengths and weaknesses of the ARGOS-SC system. At V13 (Month 36), the investigator responsible for IOP measurement as well as the patients will be asked to complete a user acceptance questionnaire for the MESOGRAPH reading device and the general measurement procedure.

The aim of these questionnaires is to gain more information about the level of user-acceptance of the ARGOS-SC system during implantation and during IOP measurement. The data collected with these questionnaires is only of exploratory nature and will not be included in the analysis. Results will provide the sponsor with data that could influence future device system improvements.

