### **IOP measurement in the clinic**

IOP measurement will be conducted as a series of 2x GAT (in case of a difference of more than 2mmHg, a third GAT-measurement is required) followed by 3x ARGOS-SC system. When series of measurements are made, GAT must always be used first to avoid potential operator bias. For the ARGOS-SC measurements the patient has to stay in the same position as for the GAT-measurements (chin on chin rest, forehead installed).

Additionally (if available), a series of 2x DCT (in case of a difference of more than 2mmHg, a third DCT-measurement is required) followed by 3x ARGOS-SC will be performed after the series of GAT and ARGOS-SC measurements. For the ARGOS-SC measurements, the patient has to stay in the same position as for the DCT-measurements (chin on chin rest, forehead installed).

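### GAT-first hides the paired same-session ARGOS-SC value but does not stop the tonometry operator from knowing the patient's recent home sensor level

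*Protocol*

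**What the plan says.** **The bias control.** Protocol 8.1.2 gives the aim, "To prevent possible influence of prior knowledge of the IOP value obtained with the ARGOS-SC, which is objectively displayed", and the means: "measurements will always be made first with GAT/DCT". The clinic procedure in 8.3.12.13 repeats it: "GAT must always be used first to avoid potential operator bias".

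**Access to home readings.** Home measurements are due at least four times a day, including one after getting up (8.3.11, 8.3.12.13). They are sent to a database, and "Investigators can log into the database in order to track the pressure levels of their patients as required". The same permission stands in the home-measurement part of 8.3.12.13, in footnote 11 of Protocol Table 4 and in footnote 11 of SAP Table 1. Protocol 3.4 adds that the treating ophthalmologist can see stored values on the reader during a visit. At each visit site staff "download all readings recorded since the last visit" (8.3.11), with no statement that this follows tonometry.

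**Who measures.** Protocol 8.3.12.13 assigns GAT and DCT to as few dedicated investigators as possible at each site. Section 11.12 says the study is open-label and not masked.

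**Susceptibility of GAT.** Protocol 3.3 describes GAT as "prone to operator biases such as digit bias and bias towards the norm".

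**Self-measurements in the SAP.** SAP section 9 lists as a change from the protocol that ARGOS-SC self-measurements were not recorded, without saying where.

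**The concern.** The protocol chose to protect the GAT reading from knowledge of the sensor, and its only means of doing so is the order of measurement within the session. That order does not cover knowledge brought into the session. A home value from the same morning may already be in the database or on the reader, and the role that may look at it is the role that performs tonometry.

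GAT is the main reference for the primary endpoint. A reference reading drawn toward the device under test shrinks the differences, so any such influence would favour the device. In a long-term study it could also mask part of a sensor drift. The current plan keeps no record of who viewed home values before measuring, so the analysis could not separate exposed from unexposed pairs.

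**Working it through.** There is no figure in the plan to reproduce. The point is procedural, and the arithmetic only shows scale.

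**Step 1: what the documents protect and what they leave open (Protocol unless stated).**

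| Knowledge the operator might have | Protected? | Where |
|---|---|---|
| Paired ARGOS-SC value, before GAT | Yes, by order | 8.1.2, 8.3.12.13 |
| Home values in the database | No limit stated | 8.3.11, 8.3.12.13, Table 4 fn 11; SAP Table 1 fn 11 |
| Home values on the reader at the visit | No limit stated | 3.4 |
| Home values from the visit download | Timing not stated | 8.3.11 |
| Same-visit ARGOS-SC values, before DCT | No: DCT follows the first ARGOS-SC series | 8.3.12.13, Table 4 fn 10 |

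No provision separates the operator from the person who reviews home values. Sections 4.6, 6.1 and 8.3.12.13 limit the use of sensor values for treatment decisions; they do not limit viewing them.

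**Step 2: model for scale.** Let D be the sensor value at the visit minus an uninfluenced GAT reading, w the share by which GAT is pulled toward the recalled home level, and e the visit sensor value minus that home level. Recorded GAT = GAT + w × (home level − GAT), so

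recorded difference = (1 − w) × D + w × e.

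With e = 0 and D normal with mean 0, the share within 5 mmHg is 2Φ(5 / (SD × (1 − w))) − 1.

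From the documents: the 5 mmHg band and the 65% benchmark (9.1.4). Assumed: the SDs, normality, zero mean offset, e = 0, and w.

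| Assumed true SD | w = 0 | w = 0.1 | w = 0.2 |
|---|---|---|---|
| 6 mmHg | 5/6.0: 59.5% | 5/5.4: 64.6% | 5/4.8: 70.2% |
| 5 mmHg | 5/5.0: 68.3% | 5/4.5: 73.3% | 5/4.0: 78.9% |

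At SD 6, a 10% pull still falls just short of 65%; a 20% pull passes it.

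**Step 3: home level not equal to the visit value.** Letting e vary with an assumed SD of 0 to 4 mmHg changes little. From a true share of 60% (SD 5.94), w = 0.1 gives 64.9% to 65.0% and w = 0.2 gives 70.0% to 70.7%.

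**Step 4: drift.** Section 4.7.1.4 specifies annual drift of at most 2.5 mmHg. At that limit, 24 months give 2.5 × 2 = 5 mmHg. With an assumed SD of 3 mmHg, w = 0.2 would show an offset of 0.8 × 5 = 4 mmHg and raise the share within 5 mmHg from 50.0% to between 65.3% and 66.1%, for the same range of e.

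**The case against.** The best counter-argument is that the order rule does its stated job for GAT. The value it guards against is the one on display in the session, and GAT is taken before that appears. Home values are earlier readings of a pressure that, by Protocol 3.3, fluctuates with activity and time of day. This stands, and it limits the point to knowledge of the recent sensor level.

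A reader might infer that GAT readings are biased, that agreement is inflated, or that analysis could never address it. The documents support none of these. They do not show that any operator looked or that any reading moved. The GAT biases named in 3.3 are digit bias and a pull toward the norm, so they show susceptibility but not a pull toward another device. Because treatment decisions rest mainly on tonometry, operators have a clinical reason to read it accurately. Keeping the number of operators small is itself a bias control. Recording viewing status would also permit a sensitivity analysis.

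On who measures, 8.3.12.5 mentions "the investigator responsible for IOP measurement as well as the patients", but in a questionnaire about the reader and the general procedure. The firmer text is 8.3.12.13, and even that does not say that the person who measures is the person who logs in.

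SAP section 9 could weaken the point further. If it means that no home values reached the telemetry database, the database route is largely closed, although values on the reader might still be visible. If it means only that they were not captured for analysis, the route is open.

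Finally, the study is open-label, exploratory and descriptive, with no tests planned in the SAP. That lowers the stakes but does not remove the gap between the protocol's stated aim and its means.

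**Conclusion.** The point holds as a gap in bias control. GAT-first conceals the paired value but not the recent home sensor level, which the measuring role may view without a stated limit. The size of any effect is unknown and may be zero. The illustration in which 59.5% becomes 64.6% to 70.2% rests on an assumed SD of 6 mmHg, normal differences, no mean offset, a home level equal to the visit value and a pull of 10-20%, none of which the documents supply. It shows only that a modest pull could move a result across the 65% benchmark.

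Two related matters need settling. The effect of the SAP statement on self-measurements depends on what it means. And 8.1.2, which puts both GAT and DCT first, does not match 8.3.12.13 and Table 4 footnote 10, which place DCT after the first ARGOS-SC series; for DCT, even same-visit sensor values may already be known.

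**What to change.** 1. In Protocol 8.1.2, 8.3.11 and 8.3.12.13, state that on a visit day the tonometry operator does not open the ARGOS-SC database or the reader memory until the tonometry values are written in the source record, and that the reader download follows the in-clinic IOP series at the same visit. The trigger should be source recording because 9.11 allows CRF entry after the visit.
2. Add a CRF item on whether the operator viewed home readings since the last visit, and when. This captures viewing before the visit day, which the first rule cannot prevent.
3. In SAP 8.5.1, add a descriptive sensitivity analysis of agreement by viewing status. With at most 24 patients and five visits there are at most 24 × 5 = 120 GAT pairs, so it can only be descriptive. For visits already completed without this record, state the limitation in the report.
4. In SAP section 9, say whether self-measurements are missing from the analysis data or from the telemetry database.
5. Reconcile 8.1.2 with 8.3.12.13 and Table 4 footnote 10 on the position of DCT, and state that under the current sequence the DCT comparison is not protected from same-visit sensor values.

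The cost is wording, the order of tasks within a visit, one CRF item and one descriptive table. The small downside is that home data are reviewed at the end of the visit instead of the start.
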